8.2.2 Vital Signs

Vital signs will be measured in supine position at timepoints indicated in the SoA ([Table 1](#)).

Blood pressure and participant's position during measurement; pulse; respiratory rate; temperature and location of measurement, weight, and height (at Baseline only) will be measured and recorded.

Blood pressure and pulse measurements will be preceded by ≥ 5 minutes of rest for the participant in a quiet setting without distractions (e.g. television, cell phones) and measured with an automated device. Manual techniques will be used only if an automated device is not available.

At visits where multiple assessments and procedures are to be done at the same timepoint, the vital signs should be done before blood sampling for laboratory tests.

8.2.3 Electrocardiograms

12-lead ECG will be performed at Screening only as indicated in the SoA (Table 1).

TriPLICATE 12-lead ECG will be obtained as outlined in the SoA using an ECG machine that automatically measures heart rate, PR, RR, QRS, QT, and QTcF.

8.2.4 Clinical Safety Laboratory Tests

Blood and urine samples will be collected for the clinical laboratory tests listed in [Appendix 10](#) at the timepoints listed in the SoA. All samples will be clearly identified.

Additional tests may be performed at any time during the study, as determined necessary by the Investigator or required by local regulations

The tests will be performed by a local laboratory.

The Sponsor must receive a list of the local laboratory normal ranges before shipment of study intervention(s). Any changes to the ranges during the study must be forwarded to the Sponsor.

The Investigator will review each laboratory report, document this review, and record any clinically significant changes occurring during the study as an AE, unless it does **not** meet the AE definition, as specified in [Appendix 5](#). The laboratory reports will be filed with the source documents.

Pregnancy testing (serum or highly sensitive urine) will be conducted as indicated in the SoA (see Section 1.3).

Additional serum or urine pregnancy testing may be conducted at any time during the study to establish the absence of pregnancy, at the Investigator's discretion or if local regulations require them.

8.3 Adverse Events, Serious Adverse Events, and Other Safety Reporting

- The definitions of an AE, SAE, and AESI are in [Appendix 5](#).

- The Investigator and any qualified designees (e.g. Subinvestigators) are responsible for detecting, documenting, and recording events that meet the definition of an AE, SAE, or AESI. The Investigator remains responsible for following up all AEs, as specified in Section 8.3.2.
- Requests for follow-up will usually be made via the Sponsor or CRO-designated study team member, although in exceptional circumstances the global patient safety department may contact the Investigator directly to obtain further information or to discuss the event.
- The method of recording, evaluating, and assessing causality of AEs, SAEs, and AESIs and the procedures for completing and transmitting SAE reports are in [Appendix 5](#).
- All AEs, SAEs, and AESIs will be collected from the signing of the ICF until the End of Study Visit at the timepoints specified in the SoA (Section 1.3). Beyond this reporting period, any new unsolicited SAEs that the Investigator spontaneously reports to the Sponsor will be collected and processed. All SAEs ongoing at the End of Study Visit must be monitored and followed up by the Investigator until stabilization or until the outcome is known, unless the participant is documented as “lost to follow-up”.
- All SAEs will be recorded and reported to the Sponsor or designee immediately and under no circumstance will this exceed 24 hours, as indicated in [Appendix 5](#). The Investigator will submit any updated SAE data to the Sponsor within 24 hours of it being available using the same procedure that was used for the initial report.
- Investigators are not obligated to actively solicit information on AEs, SAEs, or AESIs after the end of study participation. However, if the Investigator learns of any SAE, including a death, at any time after a participant has been discharged from the study, and he/she considers the event to be reasonably related to the study intervention or study participation, the Investigator will promptly notify the Sponsor.

8.3.1 **Method of Detecting Adverse Events and Serious Adverse Events**

At each study visit, the participant will be queried on changes in his or her condition.

During the reporting period, any unfavorable changes in the participant’s condition will be recorded as AEs, regardless of who report it (by the participant or observed by the Investigator).

Care will be taken not to introduce bias when detecting AEs, SAE, and/or AESIs. Open-ended and nonleading verbal questioning of the participant is the preferred method to inquire about AE occurrences.

The method of recording, evaluating, and assessing causality of AEs, SAEs, and AESIs and the procedures for completing and transmitting SAE reports are in [Appendix 5](#).

All SAEs must be additionally documented and reported using the appropriate Report Form as specified in [Appendix 5](#).

8.3.2

Follow-up of Adverse Events and Serious Adverse Events

After the initial AE/SAE/AESI report, the Investigator is required to proactively follow each participant at subsequent visits/contacts. All SAEs and AESIs (as defined in Section 8.3.6), will be followed until resolution, stabilization, the event is otherwise explained, or the participant is lost to follow-up (as defined in Section 7.3). Reasonable attempts to obtain this information will be made and documented. It is also the Investigator's responsibility to ensure that any necessary additional therapeutic measures and follow-up procedures are performed. Further information on follow-up procedures is in [Appendix 5](#).

8.3.3

Regulatory Reporting Requirements for Serious Adverse Events

Prompt notification by the Investigator to the Sponsor of an SAE (particularly life-threatening and deaths) is essential so that legal obligations and ethical responsibilities toward the safety of participants and the safety of a study intervention under clinical investigation are met.

The Sponsor has a legal responsibility to notify both the local regulatory authority and other regulatory agencies about the safety of a study intervention under clinical investigation. The Sponsor will comply with country-specific regulatory requirements relating to safety reporting to the regulatory authority, IRB/IEC, and Investigators.

Individual Case Safety Reports will be prepared for SUSARs according to local regulatory requirements and Sponsor policy and forwarded to Investigators within 15 days.

An Investigator or Subinvestigator who receives an Individual Case Safety Report describing a SUSAR or other specific safety information (e.g. Emerging Safety Issue Report, summary or listing of SAEs/SUSARs) from the Sponsor will read it and confirm completion of this activity. This information will be filed in the Investigator's Site File, and the IRB/IEC will be notified, if appropriate, according to applicable local laws/regulations and site SOPs.

8.3.4

Pregnancy

- Details of all pregnancies in female participants and, if indicated, female partners of male participants will be collected after the start of study intervention and until ≥ 120 days for female partners of male participants and ≥ 62 days for female participants.
- If a pregnancy is reported, the Investigator will record the pregnancy information on the appropriate form and submit it to the Sponsor within 24 hours of female participant or female partner of male participant (after obtaining the necessary signed informed consent from the female partner) pregnancy.
- While pregnancy itself is not considered to be an AE or SAE, any pregnancy complication, or elective termination of a pregnancy will be reported as an AE or SAE. Adverse pregnancy outcomes (e.g. spontaneous abortion, fetal death, stillbirth, congenital anomalies, ectopic pregnancy) are considered and reported as SAEs. A spontaneous abortion (occurring at < 22 weeks gestational age) or stillbirth (occurring at > 22 weeks gestational age) is always considered to be an SAE and will be reported as such.

- The participant/pregnant female partner will be followed to determine the outcome of the pregnancy. The Investigator will collect follow-up information on the participant/pregnant female partner and the neonate, and the information will be forwarded to the Sponsor. Generally, follow-up will not be required for longer than 6 to 8 weeks beyond the estimated delivery date for a healthy newborn. In case of a congenital anomaly or other illness of the newborn, follow-up will continue until the illness has resolved or there is a definite outcome of the event.
- Any post study pregnancy related SAE considered reasonably related to the study intervention by the Investigator will be reported to the Sponsor as specified in Section 8.3.3. While the Investigator is not obligated to actively seek this information in former study participants/pregnant female partner he or she may learn of an SAE through spontaneous reporting.
- Any female participant who becomes pregnant while participating in the study will discontinue study intervention.
- Prior to continuation of study intervention following pregnancy, the following will occur:
 - The Sponsor and the relevant IRB/IEC give written approval
 - The participant gives signed informed consent
 - The Investigator agrees to monitor the outcome of the pregnancy and the status of the participant and her offspring

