Visit Number	Prescreening	Scr + Visit 1 ^a	Visit 2 ^a	Visit 3	Visit 4	Visits 5 to 12	Visit 13	Unscheduled Visit	
^a Visit 1 and 2: Participants randomized to Cohorts 1 to 3 will remain in hospital or stay in the vicinity of the sites for 24 hours for PK sampling and assessment of parasitemia (see Table 2).
 
Participants randomized to Cohort 4, will visit the clinic on Days 1, 2, and 3 for dosing in an outpatient setting
	
Timepoint	Prescreening	Day 1	Day 2	Day 3	Day 4	Week 2 to 9 (weekly visits starting at Day 8)	EOS (last visit) Week 10, Day 64 ^b	Can be required due to AEs, and AESIs; follow-up of AEs and AESIs	
^b Day 64 or day of completion or premature discontinuation.
 
Participants will remain in the study until parasitemia or until Day 64, whichever comes first.
 
All EOS evaluations will be completed before providing antimalarial rescue treatment if required.
	
Blood films (microscopy)		X	X	X	X	X	X		
Thick and thin blood films will be collected at Visit 1 (predose) to confirm eligibility and at all visits.
 
Cohorts 1 to 3: The exact timepoints on Days 1 to 2 are provided in Table 2.
 
Cohort 4: Blood films should be examined at Screening, predose on Day 1, Day 2, and Day 3.
 
Blood sampling for parasitemia will be done simultaneously with PK.
	
Inclusion/ exclusion criteria		X								
COVID-19 antigen test		X							
The test will be conducted at Visit 1. Additional COVID-19 tests may be conducted as needed.
	
Demographic and medical history		X								
Randomization		X								

Assessments & Procedures	Outpatient	Outpatient/Inpatient ^a		Outpatient					Notes	
Visit Number	Prescreening	Scr + Visit 1 ^a	Visit 2 ^a	Visit 3	Visit 4	Visits 5 to 12	Visit 13	Unscheduled Visit	
^a Visit 1 and 2: Participants randomized to Cohorts 1 to 3 will remain in hospital or stay in the vicinity of the sites for 24 hours for PK sampling and assessment of parasitemia (see Table 2).
 
Participants randomized to Cohort 4, will visit the clinic on Days 1, 2, and 3 for dosing in an outpatient setting
	

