Timepoint	Prescreening	Day 1	Day 2	Day 3	Day 4	Week 2 to 9 (weekly visits starting at Day 8)	EOS (last visit) Week 10, Day 64 ^b	Can be required due to AEs, and AESIs; follow-up of AEs and AESIs	
^b Day 64 or day of completion or premature discontinuation.
 
Participants will remain in the study until parasitemia or until Day 64, whichever comes first.
 
All EOS evaluations will be completed before providing antimalarial rescue treatment if required.
	
M5717 plus pyronaridine dosing		X							Applicable to participants randomized to Cohorts 1 to 3. Participants randomized to Cohort 4 will not receive any treatment with M5717 and pyronaridine.	
Malarone dosing		X	X	X					Only applicable to Cohort 4. Participants randomized to Cohort 4 will receive Malarone as per SmPC on Days 1 to 3 (4 tablets once a day for 3 days).	
Physical examination		X	X	X	X	X	X	X	A complete physical examination will be done at screening and at the EOS Visit. At other time points an abbreviated examination will be performed (see Section 8.2.1).	
Neurological physical examination		X	X	X	X	X	X	X	Will be done during screening and at every visit. Details are provided in Section 8.2.1 .	

Assessments & Procedures	Outpatient	Outpatient/Inpatient ^a		Outpatient					Notes	
Visit Number	Prescreening	Scr + Visit 1 ^a	Visit 2 ^a	Visit 3	Visit 4	Visits 5 to 12	Visit 13	Unscheduled Visit	^a Visit 1 and 2: Participants randomized to Cohorts 1 to 3 will remain in hospital or stay in the vicinity of the sites for 24 hours for PK sampling and assessment of parasitemia (see Table 2). Participants randomized to Cohort 4, will visit the clinic on Days 1, 2, and 3 for dosing in an outpatient setting	
Timepoint	Prescreening	Day 1	Day 2	Day 3	Day 4	Week 2 to 9 (weekly visits starting at Day 8)	EOS (last visit) Week 10, Day 64 ^b	Can be required due to AEs, and AESIs; follow-up of AEs and AESIs	^b Day 64 or day of completion or premature discontinuation. Participants will remain in the study until parasitemia or until Day 64, whichever comes first. All EOS evaluations will be completed before providing antimalarial rescue treatment if required.	
Pregnancy test		X					X		Female participants of childbearing potential: serum test at Screening. Urine test at EOS Visit or at premature discontinuation.	

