Adaptive Aspects of Study Design	
Safety stopping criteria:
 
If one of the criteria is met, the current study will be put on hold until it has been established that the benefit-risk of the combination is optimal
 
1. Liver toxicity signals: > 1 participant present any of the following criteria:
a. Presence of Hy's law criteria (ALT and/or AST > 3 × ULN, and elevation of serum TB to > 2 × ULN, without initial findings of cholestasis [elevated serum ALP], with no other reason to explain the combination of increased transaminases and TB).b. CTCAE v5.0 ≥ Grade 3 ALT or AST increases, that do not return to normality or below 1.5 × the ULN at the end of follow-up (28 days after first treatment).c. CTCAE v5.0 ≥ Grade 3 ALT or AST increases accompanied by posttreatment established coagulation disorder at any time (INR ≥ 1.5) not related to another underlying condition.2. CNS signals:
a. if ≥ 1 participant present persistent severe study intervention-related CNS disorders considered AEs that do not resolve within 2 weeks after the onset, orb. if ≥ 2 participants present persistent severe study intervention-related CNS AEs irrespectively of the recovery status, orc. if ≥ 1 participants experience a serious study intervention-related CNS AE.3. SUSAR Grade 4 or higher according to the CTCAE v5.0.
----------------------------------	---

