	
any study intervention(s) (5 terminal half-lives of 155 hours) plus 30 days (a menstrual cycle) after the last dose of M5717, pyronaridine, or Malarone (and agree not to donate eggs [ova, oocytes] for reproduction during this period).
 
The Investigator evaluates the effectiveness of the contraceptive method in relationship to the first dose of M5717, pyronaridine, or Malarone.
 
The Investigator reviews the medical history, menstrual history, and recent sexual activity to decrease the risk for inclusion of a participant with an early undetected pregnancy.

Informed Consent	
6. Are capable of giving signed informed consent, as indicated in Appendix 3, which includes compliance with the requirements and restrictions listed in the ICF and this protocol.

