6.8.1 Rescue Medicine

The following circumstances warrant discontinuation from the study and the implementation of rescue medication:

1. Development of acute uncomplicated *P. falciparum* malaria, or severe malaria in the presence of parasitemia at any time during the study.
2. Development of acute uncomplicated *P. vivax* or other species malaria in the presence of parasitemia at any time during the study.
3. Vomiting the replacement dose within 2 hours of intake. (Note: If the participant vomits a dose within 1 hour of intake it may be replaced once).
4. Asymptomatic parasitemia after administration of study intervention should be managed as per national treatment guidelines or medical judgment.

Rescue treatment involves therapy with an effective antimalarial available locally, either ACTs, or artesunate injection based on investigator assessment of severity of malaria symptoms. Administration may be orally or parenterally depending on the participant's clinical condition.

The exact rescue regimen and route of administration must be recorded in the CRF on the concomitant medication page together with the start and end dates of the rescue medication applied. These participants will not be replaced.

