9.4.2 Safety Analyses

All safety analyses will be performed on the Safety Analysis set. The safety analyses are described in [Table 5](#).

AEs will be classified using the most recent MedDRA version at time of the analysis to determine SOC, PT, and SMQs.

Table 5 Summary of Main Statistical Analyses – Safety

Reference #	Category	Statistical Analysis Methods
Secondary		
6 - Incidence, severity, and seriousness of TEAEs, treatment-emergent study intervention related AEs, as per CTCAE v5.0	Main	Frequency and percentage of participants by SOC and PT.

TEAEs are defined as AEs which started at or after the administration of IMP (study treatment) or which started prior to the first administration of IMP but worsened after the dose intake, until the last scheduled assessment will be regarded as treatment-emergent, but before established rescue antimalarial treatment is administered, if required. Treatment-related AEs are those rated by the Investigator as “definitely”, “probably” or “possibly” related. All AEs will be documented, and will include the Investigator term, the preferred term, start, and end date of AE, duration (days), severity, drug relationship, action taken, and outcome. Liver signals (AT increase, TB increase) and CNS signals will be considered AESIs and specific follow-up will be performed, through laboratory surveillance, and a specific physical examination at specific visits during the follow-up.

Abnormal laboratory findings and other abnormal investigational findings should not be reported as SAEs unless they are associated with clinical signs and symptoms, lead to treatment discontinuation, or are considered otherwise medically important by the Investigator.

Examples of medically important findings include:

- Requirement for treatment or any other therapeutic intervention.
- Necessity for further diagnostic evaluation (excluding repetition of the same procedure to confirm the abnormality).
- Association with clinical signs or symptoms that may have a significant clinical impact, as determined by the Investigator.
- Clinically significant changes (as assessed by the Investigator) of any laboratory parameter throughout the study (compared to the last assessment prior to trial treatment).

Note: if the abnormal results were already present at baseline with the same severity, it will be recorded as medical history.

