15.1.2 The 3-Tier Approach

The 3-tier approach for summarizing and analyzing AEs in clinical studies will be followed. AEs in different tiers are analyzed using different types of statistical analysis.

The AEs identified for Tier 1 reporting are listed in below table together with the description how Tier 1 AEs will be analyzed:

Tier 1 AE	Within group summary	Between group comparison (Each dose cohort – natural infection cohort) 95% CI
Nervous system disorders (SOC 10029205)	n (%)	Δ [xx%, xx%]
ALT increased (PT 10001551)		
ALT abnormal (PT 10001547)		
AST increased (PT 10003481)		
AST abnormal (PT 10003477)		
AST/ALT ratio abnormal (PT 10082832)*		

* either documented AE or AST/ALT=abnormal in laboratory data. An AST/ALT ratio between 0.7 and 1.4 is thereby interpreted as “normal”. Values outside of this range are “abnormal”.

All Tier 1 events will be summarized in a table. Incidence rates and differences in incidence rates between each dose cohort and the natural infection cohort will be provided together with 95% CIs for the differences in incidence rates. For Tier 1 events which were observed for less than 3 participants the CIs will not be displayed in the Tier 1 table. 95% CIs for the differences in incidence rates will be estimated using Miettinen & Nurminen method. For graphical illustration a forest plot will be provided separately for the different treatment cohorts.

All TEAEs for which any PT or SOC is observed in 4 or more participants in any cohort are defined to be Tier 2 AEs. Tier 2 AEs are thus used for signal detection among common events. A frequency table by SOC and PT will be provided together with differences in incidence and 95% CI comparing different dose groups to the natural infection cohort. While analyses will be done for all Tier 2 TEAEs, only TEAEs with incidence proportion $\geq 5\%$ in at least one cohort will be presented in the body of CSR. No multiplicity adjustment will be applied.

Remaining TEAEs are defined as TIER 3 AEs and frequencies of participants with at least one Tier 3 TEAE will be provided by SOC and PT.

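### Safety observation ends with the efficacy outcome, yet the SAP compares crude AE proportions with Cohort 4, the cohort expected to leave earliest

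*Protocol*

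**What the plan says.** **When observation ends.** Note b to the Schedule of Activities (Protocol Section 1.3, Table 1) reads: "Participants will remain in the study until parasitemia or until Day 64, whichever comes first". Under Protocol Section 4.4, a participant whose parasitaemia recurs attends the EOS Visit at that point and counts as having completed the study. Section 6.8.1 adds: "The following circumstances warrant discontinuation from the study and the implementation of rescue medication". Its list includes clinical malaria with parasitaemia and vomiting of a replacement dose.

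**What stops then.** Section 8.3 says: "All AEs, SAEs, and AESIs will be collected from the signing of the ICF until the End of Study Visit". It adds that investigators need not actively solicit events afterwards. The liver tests and neurological examinations in Table 1 are tied to the same visits.

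**How AEs are compared.** SAP 9.3 bases proportions on the number of participants in the analysis set. SAP 15.1.1 lists frequency tables. For Tier 1 events, SAP 15.1.2 plans "Incidence rates and differences in incidence rates between each dose cohort and the natural infection cohort", with Miettinen and Nurminen intervals, and Tier 2 events are compared with the same cohort. The SAP text available describes no person-time or time-to-event analysis of AEs.

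**Two related wordings.** Protocol 9.4.2 closes the TEAE period at the last scheduled assessment, "but before established rescue antimalarial treatment is administered, if required". SAP 15.1 gives a start to that period but no end. Separately, liver stopping criterion 1b in Protocol Section 4.1 judges recovery "at the end of follow-up (28 days after first treatment", whereas follow-up elsewhere runs to Day 64 or recurrence.

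**The concern.** A participant who stays parasite-free is asked about AEs, examined and sampled for 63 days. One who recurs early is not. Protection is what the treatments are meant to change, so the length of safety observation differs systematically by cohort. A crude difference in proportions then mixes drug effect with time at risk.

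The Tier 1 terms are nervous system disorders and ALT/AST abnormalities, which are the areas of special interest. One Tier 1 row also counts any AST/ALT ratio outside 0.7 to 1.4 in the laboratory data, so each extra scheduled draw is another chance to be counted.

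The same mechanism could distort comparisons between M5717 doses. If a higher dose protects longer, it is also watched longer, and an AE trend with dose could be partly an artefact. Protocol Section 4.2 says the study is to support the choice of dose regimen.

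The disposition table will not reveal the imbalance, because participants with recurrence are classed as completers.

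**Working it through.** **Inputs.** Protocol Section 9.2 gives 63% free of parasitaemia for Cohort 4 (observed at Day 70 in a placebo-controlled field study), 87% for the top dose over 63 days, HR 0.29, 21 events, 80% power and 192 randomised (48 per cohort). The AE risks below are assumptions, because the documents give none.

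**1. The plan's own figure.** Schoenfeld events, two-sided 0.05 and 80% power: 4 × (1.960 + 0.842)² / (ln 0.29)² = 20.5, so 21. Power at 21 events is 0.81. The planning rates are therefore used as stated.

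**2. Hazards of leaving, taken as constant.**
- Cohort 4: −ln(0.63)/70 = 0.00660 per day
- Top dose: −ln(0.87)/63 = 0.00221 per day

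**3. Mean follow-up**, (1 − exp(−63h))/h.
- Cohort 4: 51.5 days
- Top dose: 58.8 days, a ratio of 58.8/51.5 = 1.14

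The share leaving by 28 days is 1 − exp(−28h): 16.9% and 6.0%, or about 8 and 3 of 48.

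**4. Crude AE risk when the true risk is equal.** With AE hazard a, observed risk = a/(a+h) × (1 − exp(−63(a+h))). For a true 63-day risk of 30%, a = −ln(0.70)/63 = 0.00566.
- Cohort 4: 0.00566/0.01226 × (1 − exp(−0.772)) = 24.8%
- Top dose: 0.00566/0.00787 × (1 − exp(−0.496)) = 28.1%
- Spurious difference: 3.3 points

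At a true risk of 50% the figures are 41.9% and 47.0%, a difference of 5.2 points.

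**5. If AEs occur early.** With a 20% risk confined to the first 14 days, a = −ln(0.80)/14 = 0.01594, and 63 is replaced by 14 in the formula. The difference is 0.6 points, or 0.7 if the 63% is read as a Day 63 rate.

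**6. Against precision.** 1.96 × √(0.248×0.752/48 + 0.281×0.719/48) = 0.176, a half-width of about 18 points. The 3.3-point artefact is 3.3/17.6, just under one fifth of it.

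**7. Sensitivity.**
- Reading the 63% as a Day 63 rate, as the plan's HR calculation does, follow-up is 50.5 and 58.8 days (ratio 1.17). The spurious difference is 1.3, 2.6, 3.8 and 5.9 points at true risks of 10%, 20%, 30% and 50%.
- With the same reading and exit only at weekly visits, follow-up is 51.8 and 59.3 days.
- Over other assumed pairs of Day 63 rates (Cohort 4/top dose), the follow-up ratio runs from 1.06 (80%/90%) to 1.45 (40%/90%).

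Dropout and the few days to clearance are ignored. No rates are given for the two lower doses, so the between-dose effect cannot be sized from the documents.

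**The case against.** The case for leaving the plan alone has real force.

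- **The bias is small and conservative against Cohort 4.** It makes M5717 look worse. After a single dose, many AEs may be early, which brings the artefact below one point. The study is exploratory and descriptive (Protocol 9.1). All of this stands, and it limits the weight of the point.
- **Liver safety has other outputs.** SAP 15.2.5 plans laboratory summaries over time, individual plots, shift tables and an eDISH plot. This also stands, although none of these adjusts the AE comparisons.
- **The two TEAE definitions will rarely disagree.** EOS evaluations precede rescue and AE collection ends at EOS, so few post-rescue events should exist. This stands.

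A reader might also infer more than the documents support.

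- *That follow-up of liver and CNS events is cut off.* Protocol 8.3.2 follows SAEs and AESIs already detected to resolution or stabilisation, and Appendix 6 follows possible DILI to normal or Baseline. Unsolicited new SAEs are still accepted after the study. What is lost is scheduled detection of new events.
- *That pregnancy follow-up is cut off.* Only the test moves: "Urine test at EOS Visit or at premature discontinuation". Section 8.3.4 sets collection at 62 days or more for female participants and 120 days or more for partners, whatever the EOS date.
- *That observation falls short of drug elimination.* Section 5.1 cites "5 terminal half-lives of 155 hours", which is 5 × 155/24 = 32.3 days. A participant followed to Day 64 has 63 days. Most early leavers are expected in Cohort 4, which receives no M5717 and whose drugs have quoted half-lives of at most 3 days. In the top dose about 7% (3 of 48) would leave before 32.3 days.
- *That an exposure-adjusted analysis was planned and dropped.* The SAP abbreviates an adverse event incidence rate and does not use it, but the same list contains Stable Disease, so template carry-over is as likely.

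**Conclusion.** The point holds at the level of analysis. The length of safety observation depends on the efficacy outcome, and the planned AE comparisons do not allow for it. On the plan's rates, the top dose is observed about 14% to 17% longer than Cohort 4. A spurious M5717 excess of about 3 to 4 points follows at an evenly spread 30% risk, and less than one point if a 20% risk falls in the first 14 days.

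These sizes rest on constant hazards for both parasitaemia and AEs. If protection is strong early and then wanes, fewer M5717 recipients leave early than assumed here. The documents do not support saying that harm on M5717 is hidden in the comparison with Cohort 4, because the direction is the opposite. Between doses, distortion is possible but cannot be sized.

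The differing TEAE definitions and the two meanings of end of follow-up are genuine inconsistencies. The first should have little numerical effect. The second leaves unclear how criterion 1b applies to a participant who exits before 28 days.

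**What to change.** 1. **SAP 15.1.1 and 15.1.2.** For TEAEs, AESIs and Tier 1 and Tier 2 events, keep the crude tables and add summaries that allow for observation time. These are a table over a fixed early window that ends before most exits, plus Kaplan-Meier cumulative incidence or exposure-adjusted rates, with differences from Cohort 4. The cost is a few tables from data already collected. Exposure-adjusted rates assume a constant hazard and so should not stand alone. Kaplan-Meier estimates assume that leaving is unrelated to AE risk.

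2. **Protocol 9.4.2 and SAP 15.1.** State one rule for the end of the TEAE period in both documents and show any post-rescue events separately. This is wording only, with minor effect.

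3. **Protocol 4.1, criterion 1b, against Sections 1.3 and 4.4.** Reconcile end of follow-up at 28 days with follow-up to Day 64 or recurrence, and say how the criterion is read for a participant who has already left. Which reading is right is for the sponsor to decide. This point proposes no change to participation, rescue or stopping rules.
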